- **Aim 3**: To explore the impact of digital CBT-I on birth outcomes. In response to research indicating that insomnia and poor sleep quality are associated with increased risk for preterm birth, we will compare rates of preterm birth, as well as other birth outcomes such as low birthweight, delivery method, and APGAR scores, between digital CBT-I and TAU participants. Because the sample size of the proposed study will be too small to draw conclusions, this aim is exploratory.

Trial Design

The study is a parallel group, superiority, randomized controlled trial of digital CBT-I versus TAU among pregnant women, with a 1:1 allocation ratio.

Methods

Participants, interventions, and outcomes

Study setting. All study activities will occur remotely via phone, website, and digital app.

Eligibility criteria. Inclusion criteria are: 1) self-reported pregnancy up to 28 weeks gestation, 2) 18 years of age or older, 3) meets DSM-5 criteria for insomnia disorder as determined by the Sleep Condition Indicator (women experiencing symptoms \geq 1 month are eligible in contrast to DSM-5 criteria requiring symptom duration \geq 3 months) or experiencing elevated insomnia symptom severity as determined by a total score \geq 11 on the Insomnia Severity Index, and 4) has regular access to a web-enabled computer, tablet, or smart phone. Exclusion criteria are: 1) probable major depression as determined by a total score \geq 15 on the Edinburgh Postnatal Depression Scale (EPDS), 2) self-reported bipolar disorder, 3) self-reported history of psychosis, 4) active suicidality defined as scoring > 1 on EPDS item 10, or report of a specific suicide plan or recent attempt, and 5) shift work employee.

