Outcomes. The primary outcome is change in insomnia symptom severity (Insomnia Severity Index) from baseline to 10-weeks post-randomization. Secondary sleep outcomes include sleep efficiency (sleep diary), sleep duration (sleep diary), global sleep quality (Pittsburgh Sleep Quality Index), and insomnia caseness (Sleep Condition Indicator). Secondary mental health outcomes include depressive symptom severity (Edinburgh Postnatal Depression Scale) and anxiety (Generalized Anxiety Disorder Scale). We will additionally examine change to 18-weeks post-randomization, 36 weeks gestation, 3 months postpartum, and 6 months postpartum. Other, exploratory outcomes include birth outcomes, such as gestational age at delivery, APGAR scores, birthweight, and delivery method.

Participant timeline (See Figure). *Eligibility survey.* Individuals interested in participating will complete an electronic consent form describing the screening procedures. Next, participants will complete questionnaires to assess eligibility. Participants will complete a demographic measure, provide contact information, and indicate whether they agreed to be contacted for other research studies. Individuals who pass the eligibility survey will complete the study consent form and be given instructions to complete the sleep diaries.

Sleep diaries. Participants will receive email requests to complete sleep diaries on REDCap for seven consecutive days. Participants will indicate when they got in bed, how long it took to fall asleep, number of awakenings, duration of awakenings, final awakening time, and when they got out of bed. Participants who complete at least four diaries will be eligible to proceed to the orientation session.

Orientation. The primary goal of the phone orientation session, modeled after Goldberg and Kiernan (2005),¹⁵ is to promote participant retention by discussing the importance of the trial, required commitments, what to expect if randomized to digital CBT-I or TAU, the rationale of the control condition and random assignment, and the impact of attrition bias. Participants will describe personal pros and cons for participating in the trial, and will be given as much time as needed to decide whether to participate.

Baseline measures. Participants will complete baseline measures on the Qualtrics online survey system.

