Randomization. Upon the participant's completion of the baseline measures, study staff will request the condition assignment from the independent investigator who generated the randomization sequence. Study staff will inform participants of their condition assignment by phone call and email.

Follow-up assessments. Participants will complete all study measures and the daily sleep diaries at 10-weeks post-randomization, and all study measures at 18-weeks post-randomization, 36 weeks gestation, 3 months postpartum, and 6 months postpartum.

Sample size. Existing literature comparing CBT-I to treatment as usual suggests a large effect size (Cohen's d=0.95) for baseline to post-intervention differences and a medium effect size (Cohen's d=0.69) for baseline to 8-week follow-up on sleep efficiency.¹³ As for depression symptom severity, existing literature comparing CBT-I to treatment as usual suggests a small to medium effect size (Cohen's d=0.20-0.69) for baseline to post-intervention differences and a medium effect size (Cohen's d=0.48-0.78) for baseline to 8-week follow-up.^{9,14} Using G*Power for an ANOVA repeated measures with a within-between interaction, we estimated that 128 women were required to have 80% power to detect a small-to-medium effect size (Cohen's d=.30) with α =.01 for a within-between interaction. Attrition in web-based CBT-I programs ranges from 4-22%.^{13,16,17} but a meta-analysis of computer-based treatments for depression estimated drop-out rates of 38.4% in programs that offer administrative support. ¹⁸ We used the higher attrition estimate of 38%, yielding a required sample size of 208 participants (n=104 per group).

Recruitment. We will utilize several recruitment methods to meet our target sample size. Although recruitment will focus mainly on the Bay Area, participants can enroll from anywhere because all study activities are completed remotely.

UCSF Outpatient Recruitment Program. Study recruiters will review medical records of women receiving prenatal care at UCSF. Women who may be eligible based off chart review (e.g., less than 28 weeks pregnant) will be approached in the clinic waiting area at the time of their appointment to be introduced to the study. Recruiters will give the patient an opt-in card

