Data collection methods. Participants will complete study measures using the Qualtrics amd REDcap survey systems, which allow participants to read questions on the screen and press the response buttons to answer. Response validation will be utilized so that participants can only enter values within range for each item. To reduce missing data, responses will be requested for each item.

Subjective sleep outcomes. The primary efficacy outcome is insomnia symptom severity, as measured by the total score on the Insomnia Severity Index (ISI). 21,22 The ISI is a seven item measure that assesses symptom severity, satisfaction with sleep, impairment caused by symptoms, distress caused by symptoms, and the extent to which others have noticed symptoms over the last two weeks. A total score is computed by summing all items. Scores ≤ 7 indicate no

clinically significant insomnia, 8-14 indicate subthreshold insomnia, 15-21 indicate moderate severity insomnia, and \geq 22 indicate severe insomnia.

Secondary sleep outcomes are sleep efficiency, nightly sleep duration, global sleep quality, and insomnia diagnosis. Daily sleep diaries will be used to measure sleep efficiency and sleep duration. Sleep efficiency is calculated by dividing the amount of time sleeping in bed by the total amount of time spent in bed and multiplying by 100. Scores range from 0-100%, with 85% and above considered normal. Sleep duration is the total amount of nightly sleep in hours. Global sleep quality will be measured using the Pittsburgh Sleep Quality Index (PSQI), a 19-item measure comprised of seven components assessing sleep duration, disturbance, latency, efficiency, quality, days of dysfunction due to sleepiness, and needing medication to sleep. ²³ Each component score ranges from 0-3, and the components are summed to create a PSQI global sleep quality score ranging from 0-21. Higher scores indicate worse global sleep quality, and scores above 5 indicate poor sleep. To measure possible cases of DSM-5 insomnia disorder, we will use the Sleep Condition Indicator (SCI). ²⁴ By adding a ninth item to assess early-morning awakening, the Sleep Condition Indicator can be used to identify possible cases of DSM-5 insomnia disorder. ²⁴

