Participants will be sent reminders via their preferred method of communication after 3, 5, and 10 days of non-response. After 2 weeks of non-response, we will contact their secondary contact person. After 3 weeks of non-response, we will mail the primary outcome measure with a stamped and addressed return envelope. Every effort will be made to obtain outcome data from

participants who discontinue the intervention. If need be, participants who discontinue the intervention can opt to only complete the primary outcome measure to reduce time burden.

Data management. Qualtrics maintains data behind a firewall. All data is accessed only by the owner of the survey who must provide a user ID and a password. All pieces of data are keyed to that owner identification and cannot be accessed by anyone else.

REDcap is housed in a locked and guarded data center staffed at all hours. Entrance to the data center requires use of a card key to unlock the data center door and a second card key lock secures the cage that the servers reside within. The security of the data center is further protected by an Operations desk that is staffed 24x7 and by a security camera system. REDcap servers are guarded by multiple firewall and intrusion detection systems. All electronic connections to the REDcap environment are encrypted. The REDcap production system is comprised of a web server front-end and a MySQL database server back-end. The web server resides in a demilitarized zone to ensure that survey participants are able to access REDcap surveys from any device connected to the Internet. The MySQL server back-end resides in the protected ISU subnet that is protected by UCSF maintained firewalls. The data stored in the REDcap MySQL database server can be accessed by the REDcap end users by logging in and opening the REDcap project(s) that they have been granted access to by the owners of the projects. Only ITS and ISU system administrators are authorized to access the back-end database server directly by logging into the virtual private network for the database server resides in.

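### The 18-week visit pools pregnant and postpartum women and the 36-week survey can fall before earlier-listed visits, but the follow-up analysis has no gestational-age term

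*Combined protocol and SAP*

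**What the plan says.** Eligibility criteria admits women with "self-reported pregnancy up to 28 weeks gestation". It gives no lower limit and does not say whether the limit applies at screening or at randomization. Between the two come a diary week ("Participants will receive email requests to complete sleep diaries on REDCap for seven consecutive days") and an orientation call after which women "will be given as much time as needed to decide whether to participate".

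Outcomes sets the primary endpoint on the randomization clock: "The primary outcome is change in insomnia symptom severity (Insomnia Severity Index) from baseline to 10-weeks post-randomization". It then adds: "We will additionally examine change to 18-weeks post-randomization, 36 weeks gestation, 3 months postpartum, and 6 months postpartum". Follow-up assessments repeats the schedule: after the 10-week assessment come "all study measures at 18-weeks post-randomization, 36 weeks gestation, 3 months postpartum, and 6 months postpartum". Two visits therefore run from randomization, one from gestation and two from delivery.

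Statistical methods specifies a linear mixed model with time, group, their interaction and a random intercept. Time is in weeks for the primary analysis, and the secondary outcomes use the same scale. Change to the later follow-ups gets one closing sentence. The text gives no visit windows, no rule for visits that coincide or reverse, and no term for gestational age or for being pregnant or postpartum. The participant timeline figure is not reproduced in the text available for review, so a rule shown only there cannot be excluded.

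**The concern.** A visit label should denote a comparable occasion for everyone it covers. Here the 18-week label covers some women in mid or late pregnancy and others several weeks after birth. The 36-week label covers some women who are months past the six-session program and others who have not yet reached the primary assessment.

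What is at stake is the reading of the secondary time points. Sleep with a newborn is likely to differ from sleep in pregnancy for reasons unrelated to the intervention. If the 18-week group difference is small, the benefit may have faded, or a sizeable share of the sample may have been measured in a period when the program has less room to act. The planned model gives one answer for both. Likewise, a 36-week result read as durability of the 10-week effect would be misread for the latest entrants.

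**Working it through.** The plan states no figure to reproduce. The check is calendar arithmetic.

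**Inputs from the plan.** Upper entry limit 28 weeks (Eligibility criteria); visits at 10 and 18 weeks after randomization and at 36 weeks of gestation (Outcomes, Follow-up assessments).

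**Assumed inputs.** Gestational age at delivery *b* is 37 to 42 weeks for the thresholds, and normal with mean 39 and SD 2 for the shares. Entry is uniform from 8 or from 14 weeks up to 28. The plan gives no entry distribution and no planning value for delivery.

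**Formulas.** Let *g* be gestational age at randomization, in weeks.
- The 10-week visit falls at gestation *g* + 10 and the 18-week visit at *g* + 18.
- The 36-week survey falls 36 − *g* weeks after randomization.

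**Order of visits (no outside assumption).**
- 36-week survey on or before the 10-week survey: 36 − *g* ≤ 10, so *g* ≥ 26.
- 36-week survey on or before the 18-week survey: 36 − *g* ≤ 18, so *g* ≥ 18.

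| *g* | Gestation at 10-week visit | 36-week survey, weeks after randomization | *g* + 18 |
|---|---|---|---|
| 12 | 22 | 24 | 30 |
| 18 | 28 | 18 | 36 |
| 22 | 32 | 14 | 40 |
| 26 | 36 | 10 | 44 |
| 28 | 38 | 8 | 46 |

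A woman screened at 28 weeks and randomized a week later (*g* = 29) reaches the 36-week survey at week 7, three weeks before the primary visit.

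**Pregnant or postpartum at 18 weeks.** The visit is postpartum when *g* + 18 > *b*, that is *g* > *b* − 18. The threshold is 19 for *b* = 37, 22 for *b* = 40 and 24 for *b* = 42. At *g* = 28 the visit is 46 − *b* = 9, 6 or 4 weeks after delivery.

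**Illustrative shares.** With mean delivery at 39 weeks the threshold averages 39 − 18 = 21.
- Postpartum at 18 weeks: (28 − 21)/(28 − 8) = 35% for entry over 8 to 28 weeks; 7/14 = 50% for 14 to 28. A simulation with SD 2 gives 35.1% and 49.9%.
- With every delivery at 40 weeks and entry over 8 to 28: (28 − 22)/20 = 30%. At 37 weeks: 9/20 = 45%. At 42 weeks: 4/20 = 20%.
- 36-week survey on or before the 10-week survey (*g* ≥ 26): 2/20 = 10%, or 2/14 = 14%.

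**Does a baseline split separate the two states?** For women randomized at 20 to 28 weeks the same simulation gives about 82.5% postpartum at 18 weeks. With entry over 8 to 28 weeks, the share *x* among those at 20 weeks or below solves 12*x* + 8(0.825) = 20(0.351), so *x* = 0.42/12, about 3.5%. A cut at 20 weeks thus separates mostly pregnant from mostly postpartum women, though not perfectly.

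**The case against.** The strongest reply is that nothing here damages the trial's main result. The primary endpoint is timed only from randomization. Randomization balances gestational age between arms in expectation, so the 10-week contrast is unbiased and the 18-week contrast is a valid randomized average over whatever mix of women is enrolled. That stands.

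Using both a gestational and a randomization clock is also a legitimate choice, because the two answer different questions, and the text does not say that the 36-week visit follows up the 10-week result. That stands too; the plan only needs to report it accordingly.

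Time in weeks would place a 36-week survey taken at week 8 at its true time. That is right if actual weeks are used, but it does not help at 18 weeks: two women at week 18 can be in different states, and no planned term distinguishes them.

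A reader might infer that crowded surveys endanger the primary outcome. For women randomized between 24 and 28 weeks, the 10-week and 36-week surveys lie at most two weeks apart, and the ISI asks about "the extent to which others have noticed symptoms over the last two weeks". Reminder sequences ("Participants will be sent reminders via their preferred method of communication after 3, 5, and 10 days of non-response") could overlap. But the documents give no figure linking this to 10-week response. Data collection methods also provides safeguards: a secondary contact, a mailed primary measure, and a primary-measure-only option for women who stop the intervention. Daily diaries are repeated only at 10 weeks. Harm to primary response is possible but not shown.

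A reader might also infer that the two explanations can never be separated. They largely can, by gestational age at randomization.

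**Conclusion.** The concern holds as an interpretation and analysis gap in the secondary time points. The order reversals (*g* ≥ 26 against the 10-week survey, *g* ≥ 18 against the 18-week survey) follow from the plan alone. The mixing at 18 weeks needs an assumed delivery date, but some entrants fall on each side of the threshold for any delivery between 37 and 42 weeks. How many is uncertain: about 35% to 50% postpartum under the two entry ranges with delivery around 39 weeks, and 20% to 45% if entry is uniform over 8 to 28 weeks and all deliver at a single date between 42 and 37 weeks. The actual entry distribution would settle this. The documents do not support a claim of bias in the primary contrast or of invalidity in the 18-week average.

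**What to change.** Change Statistical methods for the follow-up analyses:

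1. Treat visit as categorical, and add gestational age at randomization and its interaction with visit. This adjusts for a variable that is likely prognostic at 18 weeks.
2. Report the 18-week group difference overall and by gestational age at randomization, for example at or below 20 weeks and above 20 weeks, or through a group-by-visit-by-gestation term. The gestation-by-visit term alone does not let the treatment effect vary. This is a baseline split, so it preserves randomization; a split on observed delivery status would not have that guarantee.
3. Describe the 36-week result as late-pregnancy status at a varying time since randomization (8 weeks or less for the latest entrants), not as follow-up of the 10-week result. Do not label a survey completed after delivery as a 36-week-gestation survey.
4. When two dates coincide, one completed survey may serve both visits, without being counted as two independent observations.

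A rule that moves the 36-week survey to a nearby post-randomization date is not advised. For *g* of 18 to 20 and 26 to 28 it would shift the survey to 36 to 38 weeks. With delivery normal (39, 2), on average about 17% of those women would have delivered, against 6.7% at 36 weeks.

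The cost is a few lines of analysis text, using gestational age at entry, which the eligibility limit and the 36-week visit already require. The 18-week subgroup estimates are less precise and remain secondary. Protocol Amendments records 183 of 208 women randomized by March 2018, so the analysis text is the realistic place for the change.

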Statistical methods. Independent samples t-tests and chi-square tests will be used to examine between-group differences in baseline sociodemographic and clinical characteristics. Linear mixed effects models will be used to examine whether within-woman changes in sleep and mental health outcomes differ between the digital CBT-I and treatment as usual groups. 30 Models will include the sleep and mental health outcomes as the dependent variables, along with time, intervention group, and time by group interactions as the predictors. The models also will include random intercepts to accommodate the correlation among the repeated responses within women. The regression coefficients of time by intervention group interactions measure the differences in the rate of within-woman change in the outcomes between the two intervention groups. We will assess the statistical significance of the time by intervention group interaction using likelihood ratio tests. The primary analysis will assess differences in changes in insomnia symptom severity from baseline to post-intervention with time measured in weeks. Secondary analyses of additional sleep and mental health outcomes will use the same time scale. Additionally, we will examine change from baseline to follow-up.

Monitoring

Harms. Adverse events that are spontaneously reported by participants will be characterized by an independent safety officer as unexpected or expected, and causes will be characterized as definitely related, probably related, possibly related, or unrelated to study participation. Adverse events that are determined to be unrelated to study participation are documented but not reported to the IRB. All other adverse events are reported to the IRB.

Ethics and Dissemination

Research ethics approval

The research protocol will be submitted to the UCSF institutional review board for approval.

Protocol amendments

Protocol modifications will be communicated to all study investigators and approved by the IRB prior to implementation, and the trial registry will be updated accordingly.

Consent or assent

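### Sample size: 128 completers at α=.01 give about 12–34% power, not 80%, for a d=.30 between-arm difference in baseline-to-10-week change

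*Combined protocol and SAP*

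**What the plan says.** The Sample size paragraph names its procedure, "Using G*Power for an ANOVA repeated measures with a within-between interaction", and reports that "we estimated that 128 women were required to have 80% power to detect a small-to-medium effect size (Cohen's d=.30) with α =.01". It then allows for 38% attrition and arrives at 208 women, 104 per group. Trial Design specifies randomization "with a 1:1 allocation ratio", so 128 completers are 64 per arm.

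The comparison to be powered is defined elsewhere. Under Outcomes: "The primary outcome is change in insomnia symptom severity (Insomnia Severity Index) from baseline to 10-weeks post-randomization". Under Statistical methods: "The primary analysis will assess differences in changes in insomnia symptom severity from baseline to post-intervention with time measured in weeks", tested as the time-by-group interaction with a likelihood ratio test.

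The same Sample size paragraph lists effects from earlier studies: d=0.95 and 0.69 for sleep efficiency, and for depression a literature that "suggests a small to medium effect size (Cohen's d=0.20-0.69) for baseline to post-intervention differences", with 0.48–0.78 at 8-week follow-up. It gives no effect size for the Insomnia Severity Index. It also does not give the f entered, the number of measurements, the correlation between them, the G*Power effect-size option, or the SD that defines d.

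**The concern.** Eighty per cent power at α=.01 for a standardized difference of 0.30 normally takes several hundred participants unless the repeated measurements are very highly correlated, so 128 looks too small. G*Power's repeated-measures routine takes f, not d. Using the two-group conversion f = d/2 for an interaction would overstate what the sample can detect.

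As written, the sentence tells the reader that effects of 0.30 and above are covered at 80%. If they are not, a null result could be wrongly read as ruling them out. This bears most on depressive symptoms, which Objectives names as the primary outcome of Aim 2 and for which the protocol itself cites effects below 0.6.

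**Working it through.** **Inputs from the protocol.** N=128 completers, 64 per arm; α=.01, taken as two-sided because the interaction test has no direction; target power 80%; d=.30; two visits (baseline and 10 weeks).

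**Assumed, because not stated.** Correlation r between the two visits, shown at .3, .5 and .7; equal variances; d in units of the SD at a single visit, unless noted.

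**Step 1: reproduce 128.** For a within-between interaction with 2 groups and m measurements, the noncentrality is λ = f²·N·m/(1−r), with df (m−1) and (N−2)(m−1).

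- With f = d/2 = .15, m=2, r=.5, N=128: λ = .0225 × 128 × 2 / .5 = 11.52, and power is 78.0%. The N for 80% is 134.
- N is exactly 128 at m=2, r=.52, and also at m=6, r=.05. At m=3, r=.4 it is 126.
- Entering f=.30 with m=2, r=.5 gives N=36.

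So 128 is consistent with f=.15 under several settings. The actual inputs cannot be recovered from the text.

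**Step 2: what f=.15 means here.** In a 2×2 group-by-time layout, a between-arm difference in change of d SD puts an interaction effect of ±d/4 in each cell, so f = d/4. Then f=.15 is d = 4 × .15 = 0.60, and a true d=.30 is f = .30/4 = .075.

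**Step 3: power for d=.30 in the planned comparison.** With two complete visits, the interaction test compares change scores. SD of change = √(2(1−r)) and λ = (d/SD)² × 64/2. At r=.5 the SD is 1 and λ = .09 × 32 = 2.88, the same as .075² × 128 × 2 / .5.

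| r (assumed) | SD of change | λ at d=.30 | Power at d=.30 | d for 80% power | Completers needed for d=.30 |
|---|---|---|---|---|---|
| .3 | 1.18 | 2.06 | 12.3% | 0.72 | 732 |
| .5 | 1.00 | 2.88 | 18.4% | 0.61 | 524 |
| .7 | 0.77 | 4.80 | 34.0% | 0.47 | 316 |

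Simulating the planned likelihood ratio test (20,000 runs per correlation) gave 12.9%, 19.3% and 34.4%. If d is instead in SD-of-change units, power is 18.4% whatever r is. Reaching 80% at d=.30 with 128 women needs r of about .88.

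**Step 4: could another reading restore 80%?** Power at d=.30 for r=.3/.5/.7:

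| Variant | Power |
|---|---|
| One-sided α=.01 | 18% / 26% / 44% |
| Two-sided α=.05 | 30% / 39% / 58% |
| Baseline-adjusted 10-week comparison, SD √(1−r²), α=.01 | 21% / 26% / 41% |
| Omnibus interaction over six visits, constant d=.30, α=.01 | 10% / 15% / 32% |
| All 208 analysed, α=.01 | 22% / 33% / 58% |

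At the protocol's 4–22% attrition range (104 × .96 ≈ 100 to 104 × .78 ≈ 81 per arm) and r=.5, power at d=.30 is 32–25% and the detectable d is 0.49–0.54.

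**Step 5: the protocol's own cited effects** (64 per arm, α=.01, read in single-visit SD units):

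| d | Cited for | r=.3 | r=.5 | r=.7 |
|---|---|---|---|---|
| 0.48 | Depression, 8-week follow-up, low end | 38% | 54% | 81% |
| 0.69 | Sleep efficiency, 8-week follow-up | 75% | 90% | 99% |
| 0.95 | Sleep efficiency, post-intervention | 97% | 99.7% | above 99.9% |

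**The case against.** The best defence is that the software run was sound and only the label is loose. The routine takes f; if d=.30 means 2f of the interaction, power at N=128 is 78%, close to the claim. This may well be what happened, and the protocol does not rule it out. But it does not rescue the sentence. The text calls the quantity Cohen's d and sets it beside d values for treatment differences from baseline. A reader will compare them directly, whereas on this reading the powered effect is about 0.6 SD of difference in change.

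Three further points stand in part.

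- The correlation is assumed, so no single power figure can be asserted. The conclusion nevertheless holds from .3 to .7 and fails only near .88.
- The protocol does not say which SD underlies the cited effects, so the figures in Step 5 carry the same uncertainty as d=.30 itself.
- The practical consequence is limited. An effect of 0.20, the bottom of the cited depression range, has only 7% power at r=.5, but it lies below the stated target and would be underpowered even if the sentence were right. The 54% at d=0.48 assumes the full 38% attrition; with all 208 analysed it is 80% at r=.5. Depression is a secondary outcome under Outcomes, although it is primary within Aim 2.

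**Conclusion.** The stated power is wrong for the comparison the protocol defines as primary. With 128 completers at two-sided α=.01, power for a d=.30 difference in baseline-to-10-week change is 12–34% for an assumed correlation of .3–.7, and 80% power corresponds to d of about 0.72–0.47. At r=.5, effects between 0.30 and about 0.61 are presented as covered at 80% and are not.

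A d-to-f conversion suited to a two-group main effect is a plausible cause but cannot be proved from the text. The trial is not undermined: it has good power for effects as large as those cited for sleep efficiency, though no effect size is given for the Insomnia Severity Index itself. This should be corrected because it changes how null findings are read, particularly for depression.

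**What to change.** Keep the target of 208 and the planned analysis. Replace the d=.30 claim with a statement on the scale of the primary comparison, for example: 128 completers (64 per arm) give 80% power at two-sided α=.01 to detect a between-arm difference in baseline-to-10-week change of about d=0.61, in single-visit SD units, assuming a correlation of .5 (0.72 at .3; 0.47 at .7). If the investigators hold the original inputs or have a better-supported correlation, they should recompute from those.

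Report f, the number of measurements, the correlation, the G*Power effect-size option and the SD that defines d.

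This costs wording only, with no extra participants and no change in analysis. The price is a less favourable stated detectable effect (about 0.6 rather than 0.3 at r=.5) and an admission of low power for the smaller depression effects the protocol cites.
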